## 8.6. Examination of Subgroups

No subgroup analyses are planned.

## 9. SAFETY EVALUATION

### 9.1. Overview of Safety Analysis Methods

All safety summaries will be descriptive with no statistical hypothesis testing and based on the Safety Population. Patients will be summarized according to the study drug received (i.e., as treated), should it differ from the randomized treatment arm. Safety assessments will be summarized by treatment group and overall, for each Part/Period of the study. All safety endpoints will be listed in by-patient data listings.

### 9.2. Extent of Exposure

Study drug exposure will be summarized for each treatment group and overall for each Part/Period. The number of days on which study drug was dosed (at least partially), the number of days in the study exposed, and total cumulative dose will be summarized for each treatment group. The number and percentage of patients with at least one drug interruption will also be summarized.

The total number of days in the study exposed will include/ignore drug interruptions. The total number of days on study drug (excluding dose interruptions) and drug compliance will also be summarized, per Section 7.3.

### 9.3. Adverse Events

An adverse event is any untoward medical occurrence that may appear or worsen in a patient during the course of a study. It may be a new intercurrent illness, a worsening concomitant illness, an injury, or any concomitant impairment of the patient's health, including laboratory test values, regardless of etiology. Any worsening (ie, any clinically significant adverse change in the frequency or intensity of a pre-existing condition) should be considered an adverse event. A diagnosis or syndrome should be recorded on the adverse event page of the eCRF rather than the individual signs or symptoms of the diagnosis or syndrome. A worsening of the condition under study, alopecia areata, will not be reported as an adverse event.

All patients will be monitored for adverse events during the study. Assessments may include monitoring of the following parameters: the patient's clinical symptoms, laboratory, physical examination findings, or findings from other tests and/or procedures.

Adverse events will be coded using MedDRA version 23.1, and summarized by treatment group, system organ class, and preferred term for each Part/Period of the study.

An adverse event reported after informed consent, but before the first dose of study drug (i.e., Day 1), will be considered a pre-treatment adverse event. TEAEs will be defined as any adverse event that occurs after administration of the first dose of study drug in each Part/Period (ie, on or after the day of the first dose in each Part/Period). Adverse events will further be considered treatment-emergent with respect to a given Part/Period if the adverse event occurred after administration of the first dose of study drug in that Part/Period and, if the patient continues onto a subsequent period part, prior to the first dose of study drug in the subsequent Part/Period. Adverse events will be limited to those collected within this protocol (ie, for rollover patients, AEs collected under the protocol of the rollover study but not in this study will not be in this

Concert Pharmaceuticals, Inc.  
Statistical Analysis Plan – CP543.2004

study). The number and percentage of patients who report TEAEs will be summarized by treatment group, system organ class, and preferred term.

Treatment emergent adverse events will also be summarized by intensity as well as relationship to study drug.

Partial dates will be imputed for the purposes of defining TEAEs as follows:

- For a missing start day where the month and year are present, the start day will be set to the first day of the month, unless 1) the first day of the month is before the date of administration of study drug and the month and year are the same as the month and year of the date of administration of study drug, and 2) the end date is on or after the date of administration of study drug or the end date is completely missing, in which case the start day will be set to the first day of administration of study drug.
- For a missing start day and month where the year is present, the start day and month will be set to January 1st, unless 1) January 1st is before the date of administration of study drug, and 2) the end date is on or after the date of administration of study drug or the end date is completely missing, in which case the start day and month will be set to that of the first date of administration of study drug.
- For an entirely missing start date (ie day, month, and year are missing), the start date will be set to the date of administration of study drug in Part A Period 1, unless 1) the stop date is prior to the date of administration of study drug in Part A Period 1 in which case the start date will be set to the stop date, or 2) the stop date is between the start date of Part A Period 2 and the end date of Part A Period 2, in which case, the date will be set to treatment start date of Part A Period 2, or 3) the stop date is between the start date of Part B and the end date of Part B, in which case, the date will be set to the treatment start date of Part B.
- For a missing end day where the month and year are present, the end day will be set to the last day of the month, unless the month and year are the same as the month and year of the last visit date for the patient, in which case the end day will be set to that of the patient's last visit date.
- For a missing end day and month where the year is present, the end day and month will be set to the patient's last visit date, unless the year of the patient's last visit date is greater than the end year, in which case the end day and month will be set to December 31st.
- For an entirely missing stop date (i.e. day, month, and year are missing), the stop date will be imputed as the patient's last visit date.

Partial dates will be compared to the start and end dates of each Part/Period to determine the study drug administration date that will be used to be imputed.

Patients who report the same preferred term on multiple occasions will be counted once per Part/Period for the preferred term: under the highest severity when summarized by severity and under the closest relationship to study drug when summarized by relationship. Missing severity or relationship will not be imputed. If a patient reports multiple preferred terms for a system organ class, the patient will be counted only once for that system organ class.

Concert Pharmaceuticals, Inc.  
Statistical Analysis Plan – CP543.2004

The number and percentage of patients who experience TEAEs will be summarized by treatment group and overall for each Part/Period for the following:

- By system organ class and preferred term
- By severity/intensity, system organ class, and preferred term
- By relationship to study drug, system organ class, and preferred term
- Serious adverse events by system organ class and preferred term
- Serious adverse events by relationship to study drug, system organ class, and preferred term
- Adverse events resulting in discontinuation of study drug by system organ class and preferred term
- Adverse events that result in study drug dose interruption by system organ class and preferred term

The number of TEAEs (events) will also be reported. By-patient listings will include all adverse events. TEAEs will be flagged.

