Event	Day -28 to Day -1 (Visit 1)	Randomization ^{1, 2} Day 1 (Visit 2)	Week 2 (Visit 3)	Week 4, 8 (Visit 4, 5)	Week 12 (Visit 6)	Week 16, 20 (Visit 7, 8)	Week 243,4 (Visit 9)	Week 28 ⁵ (Visit 10)	Week 32 (Visit 11)	Week 36 (Visit 12)	Week 40, 44 (Visit 13, 14)	Week 484 (Visit 15)	Safety Follow-Up Visit
Informed consent	X												
Eligibility assessment	X	X											
Demographics	X												
Medical history	X	X											
Randomization		X					X^7						
PE	X	X					X					Х	X
Brief PE				X	X	X			X	X	Х		
Height	X												
Weight	X	X		X	X	X	X		X	X	X	X	X
Pregnancy test ⁸	X	X ⁹		X	X	X	X	X	X	X	X	X	
Tuberculosis test	X												
Clinical laboratory testing ¹⁰ , 11	X ¹²	X	X	X	X	X	X	X	X	X	X	X	X
Lipid assessment ¹³		X			X		X			X		X	X
HBV and HCV test	Х												
12-lead electrocardiogram	Х	X			Х		X			X		Х	X
Vital signs	X	X		X	X	X	X		X	X	Х	X	X
SALT assessment	Х	X		X	X	X	X	X^{14}	X^{14}	X^{14}	X14	Х	
Photographs	X	X		X	X	X	X	X	X	X	Х	X	
SPRO and QPRO		X			X	X	X						
CGI-S and PGI-S		X			Х	X	X						
CGI-I and PGI-I					X	X	X						
Dispense study drug		X		X	X	X	X^7	X^{15}	X^{15}	X^{15}	X15		
Pharmacokinetic blood sampling ¹⁶		X			X		X						
Study drug accountability				X	X	X	X		X	X	X	X	_
Adverse events	X				X					X			X
Concomitant medications	X		X			X				X			

PE = Physical Examination; HBV= hepatitis B virus; HCV = hepatitis C virus; SPRO = Satisfaction of Hair Patient Reported Outcome; QPRO = Quality of Hair Patient Reported Outcome; CGI-S = Clinical Global Impression of Severity; CGI-I = Clinical Global Impression of Improvement; PGI-S= Patient Global Impression of Improvement; PGI-I = Patient Global Impression of Improvement;

- ¹ Day 1 (Visit 2) may occur any time after Screening laboratory results are available and reviewed by the Investigator.
- ² For Part A, Period 1, all subsequent visits and week increments should be based on the date of Visit 2. All visit windows are ± 2 days.
- ³ Week 24 from Part A, Period 1 will also serve as the Day 1 visit for Part A, Period 2 for those who meet criteria to continue into the Dose Modification Phase.
- ⁴ Also serves as the Early Termination Visit for patient withdrawal in this period.
- ⁵ For Part A, Period 2, all subsequent visits and week increments should be based on the date of Week 24 (Visit 9). All visit windows are ±2 days.

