- The Safety Follow-Up Visit is intended as an Exit Visit for those subjects who discontinue the trial or for those who do not continue into the Open-label Extension study following completion of Part A, Period 1 or Part A, Period 2.
- ⁷Randomization and dispensation of study drug will occur on Week 24 only for those subjects who meet criteria and will continue into Part A, Period 2.
- ³ Serum pregnancy test for females of childbearing potential only. Subjects who are surgically sterile or (hysterectomy or bilateral ligation) or post-menopausal (cessation of menses for at least 12 months prior to screening) need not be tested.
- Urine pregnancy test should be performed at the randomization visit.
- ¹⁰ Includes hematology and serum chemistry, fasted.
- ¹¹ Collect pre-dose if subject is dosing in the clinic on study visit days.
- ¹² Will include thyroid stimulating hormone and hemoglobin A1c at Screening only.
- ¹³ Includes total cholesterol, low-density lipoprotein, high-density lipoprotein, and triglycerides under fasted conditions.
- ¹⁴ If SALT score >20 at any visit in Part A, Period 2, patient will enter into Part B of the study and return to their original 8 mg BID or 12 mg BID dose from Part A, Period 1. However, all safety assessments outlined in Part A, Period 2 should be performed prior to dispensing study drug in Part B.
- ¹⁵ Dispensation in Part A, Period 2 will only occur for subjects whose SALT remains \leq 20. If SALT >20, the subject should proceed to Day 1 (Visit B1).
- ¹⁶ Day 1 (post-dose) and Weeks 12 and 24 (variable times post-dose)

Table 2: Schedule of Assessments: Part B

Event	Treatment Period									
Event	Day 1 ^{1, 2} (Visit B1)	Week 2 (Visit B2)	Week 4, 8 (Visit B3, B4)	Week 12 (Visit B5)	Week 16, 20 (Visit B6, B7)	Week 24 ³ (Visit B8)	Week 28 (Visit B-SFU)			
Physical examination						X	X			
Brief physical examination			X	X	X					
Weight			X	X	X	X	X			
Pregnancy test ⁵			X	X	X	X				
Clinical laboratory testing ⁶		X	X	X	X	X	X			
Lipid assessment ⁷				X		X	X			
12-lead electrocardiogram				X		X	X			
Vital signs			X	X	X	X	X			
SALT assessment			X	X	X	X				
Photographs			X	X	X	X				
Dispense study drug	X8		X	X	X					
Study drug accountability			X	X	X	X				
Adverse events	X									
Concomitant medications				X			X			

All subsequent visits and week increments should be based on the date of Visit B1. All visit windows are ±2 days.

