11.10. Clinical Laboratory Assessments

Clinical laboratory assessments are presented in Section 18.1. Clinical laboratory samples should be collected at the beginning of each clinic visit and just prior to a dose on all Study Visit Days and will be processed by a central laboratory. In the event a patient is unable to attend an in-clinic visit due to COVID-19, clinical laboratory blood draws may be performed by a Home Health Care agency or a local laboratory. Patients should try to have laboratory blood draws performed in the morning and dose study drug after clinical laboratory blood draws are completed.

The results of clinical laboratory tests conducted at the Screening Visit (and prior to dosing) must be assessed by the Investigator to determine each patient's eligibility for participation in the study. The Investigator should indicate review of the laboratory reports throughout the study by signing and dating each report.

All clinical laboratory results that fall outside the reference range will be interpreted by the Investigator as Abnormal, not clinically significant, or Abnormal, clinically significant. Laboratory results deemed Abnormal, clinically significant will be recorded as an adverse event in the eCRF (see additional criteria outlined in Section 12.1). Clinically significant laboratory abnormalities indicative of hematologic or other effects requiring intervention should be discussed with the Medical Monitor(s). Additional tests and evaluations required to establish the significance or etiology of a clinically significant abnormal result or to monitor the course of an adverse event should be obtained when clinically indicated. Whenever possible, the etiology of the clinically significant abnormal findings will be documented on the eCRF.

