12. ADVERSE EVENTS

12.1. Definition of Adverse Event

An adverse event is any untoward medical occurrence that may appear or worsen in a patient during the course of a study. It may be a new intercurrent illness, a worsening concomitant illness, an injury, or any concomitant impairment of the patient's health, including laboratory test values, regardless of etiology. Any worsening (ie, any clinically significant adverse change in the frequency or intensity of a pre-existing condition) should be considered an adverse event. A diagnosis or syndrome should be recorded on the adverse event page of the eCRF rather than the individual signs or symptoms of the diagnosis or syndrome. A worsening of the condition under study, alopecia areata, will not be reported as an adverse event.

All patients will be monitored for adverse events during the study. Assessments may include monitoring of the following parameters: the patient's clinical symptoms, laboratory, physical examination findings, or findings from other tests and/or procedures.

An adverse event reported after informed consent, but before the first dose of study drug (ie, Day 1), will be considered a pretreatment adverse event and will be captured on the eCRF. Adverse events will be considered treatment-emergent if the onset is after the first dose of study drug.

An abnormal laboratory value is considered to be an adverse event if the abnormality:

- Is considered clinically significant; OR
- results in discontinuation from the study; OR
- is judged by the Investigator to be of significant clinical importance requiring treatment, modification/interruption of investigational product dose, or any other therapeutic intervention.

Regardless of severity grade, only laboratory abnormalities that fulfill a seriousness criterion need to be documented as a serious adverse event.

If a laboratory abnormality is one component of a diagnosis or syndrome, then only the diagnosis or syndrome should be recorded on the adverse event eCRF. If the abnormality was not a part of a diagnosis or syndrome, then the laboratory abnormality should be recorded as the adverse event. If possible, the laboratory abnormality should be recorded as a medical term and not simply as an abnormal laboratory result (e.g., record thrombocytopenia rather than decreased platelets).

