original collected data. The mean and median will be reported to an additional level of precision than the original observations, and the standard deviation will be reported to two additional levels of precision than the original observations. The precision for some original collected data and derived variables are longer than required for clinical interpretation (eg, >15 decimals). In these situations, the number of decimal places will be determined by the table of precision included as an attachment.

All efficacy summaries are descriptive with no statistical hypothesis testing. Confidence intervals and estimated treatment differences will be rounded to one additional decimal place from the original data, or a maximum of two decimal places. Standard error will be reported to an additional level of precision. Results which cannot be determined will be displayed as “NA”, “NE”, or similar.

Treatment start date for each part and period will be defined as the date of randomization or re-randomization for the respective part or period. If the treatment start date for Part A Period 2 is equal to the treatment end date for Part A Period 1 as collected on the eCRF, it will be assumed that the treatment day is associated with Part A Period 2. One day will be subtracted from the treatment end date for Part A Period 1. Similarly, if the treatment start date for Part B is equal to the treatment end date for Part A Period 2, it will be assumed that the treatment day is associated with Part B. One day will be subtracted from the treatment end date for Part A Period 2.

Date of last dose is collected on the *Treatment Discontinuation/Completion* eCRF page for each part/period. For patients with missing or partial date of last dose, or for patients who are ongoing at the time of the NDA submission, the date of last dose (ie, treatment end date) will be imputed. Date of last dose will be imputed as follows:

- For entirely missing dates for patients who are not ongoing or for partial dates where the month and day are missing, date of last dose will be imputed as the last visit date that is not a follow-up visit within a period or part.
- For partial dates where only the day is missing, the day will be imputed as the last day of the month. If this imputed date is after the treatment start date of the next part or period, or the study discontinuation date of that part or period, the day will be imputed to one day before the treatment start date of the next part or period.

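### The day-based treatment-emergent rule in SAP 9.3 charges adverse events found by pre-dose tests at a transition visit to the next treatment, which the patient has not yet taken.

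*SAP*

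**What the plan says.** SAP 9.3 defines treatment-emergent events for each Part and Period. It begins with events occurring after the first dose, then makes that operational as "ie, on or after the day of the first dose in each Part/Period". The next sentence closes the window for continuing patients: the event must also fall "prior to the first dose of study drug in the subsequent Part/Period". The same section classes events before the first dose on Day 1 as pre-treatment.

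SAP section 4 deals with a treatment date shared by two phases. At the move into Period 2, "it will be assumed that the treatment day is associated with Part A Period 2". At the move into Part B, "it will be assumed that the treatment day is associated with Part B". In each case the end date of the earlier phase goes back one day.

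The protocol makes each transition a single visit. Table 1 footnote 3 says that "Week 24 from Part A, Period 1 will also serve as the Day 1 visit for Part A, Period 2", and Table 2 footnote 2 puts Part B Day 1 on the day of the last Period 2 visit. Protocol 10.1 has the first dose of every phase taken in the clinic on Day 1. Sections 10.4.3 and 11.10 put the blood draw before dosing. For entry to Part B, Table 1 footnote 14 says that "all safety assessments outlined in Part A, Period 2 should be performed prior to dispensing study drug in Part B".

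On recording, Protocol 11.10 states: "Laboratory results deemed Abnormal, clinically significant will be recorded as an adverse event in the eCRF". Protocol 12.1 states: "Adverse events will be considered treatment-emergent if the onset is after the first dose of study drug". Protocol 12.2.4 asks for event start and stop dates and mentions no clock time.

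**The concern.** On a transition day, being after the first dose and being on the day of the first dose are not the same thing. The blood is drawn, and at the LOM visit every safety assessment is done, while the patient has taken only the old treatment. A clinically significant result must then be reported as an adverse event. If it is dated to the visit, the day rule counts it under a drug not yet taken. A cytopenia found at Week 24 after 24 weeks of 12 mg BID could appear as a Period 2 event under placebo. A finding at the LOM visit on placebo could appear as a Part B event under 8 mg or 12 mg BID.

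The Period 1 and Period 2 treatment-emergent tables are marked for the abbreviated NDA report in SAP Appendix 15.4. What is at stake is which dose carries the event in those tables.

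**Working it through.** The plan states no figure to reproduce. The check has two parts: which rule operates, and how many scheduled draws it moves.

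**Which rule operates.** Take a laboratory event dated to Week 24.

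- By sequence within the day, it precedes the first Period 2 dose. The closing sentence of SAP 9.3 and Protocol 12.1 then keep it out of Period 2.
- By calendar day, it falls on the day of the first Period 2 dose. The day clause puts it in Period 2, and section 4 allocates the shared treatment day the same way.
- Only event dates are documented, so a program can apply the second reading and not the first.
- SAP section 4 defines the Period 2 and Part B baselines as the last value on or before the day of dosing. One result can therefore be a pre-drug baseline in the laboratory tables and an event of the new drug in the adverse event tables.
- The same clause captures pre-dose findings on Period 1 Day 1, which SAP 9.3 itself calls pre-treatment.

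**Period 1 to Period 2.** Draws after Day 1 (Table 1) are at Weeks 2, 4, 8, 12, 16, 20 and 24, seven in all. Assume that laboratory-detected events are dated to the sample day and are equally likely at each draw.

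- Share of a responder's Period 1 laboratory-detected events that moves: 1/7 = 14.3%.
- Only responders continue, about 50 of 170 on 8 mg and 50 of 130 on 12 mg (Protocol 13.1). With equal event rates in responders and non-responders:
  - 8 mg: (50/170) × (1/7) = 4.2% of all laboratory-detected Period 1 events.
  - 12 mg: (50/130) × (1/7) = 5.5%.

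**Period 2 to Part B.** Draws are at Weeks 28, 32, 36, 40, 44 and 48. If LOM is found at the k-th of these, k draws were taken on Period 2 drug and the last is dated to Part B, a share of 1/k.

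| LOM visit | k | Share moved to Part B |
|---|---|---|
| Week 28 | 1 | 100% |
| Week 32 | 2 | 50% |
| Week 36 | 3 | 33.3% |
| Week 40 | 4 | 25% |
| Week 44 | 5 | 20% |
| Week 48 | 6 | 16.7% |

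**What Period 2 gains.** The Week 24 draw date enters Period 2. For LOM at the k-th visit, the draw dates assigned to Period 2 are Week 24 plus k − 1 others, so again 1/k of them precede any Period 2 drug. Without LOM the share is 1/7 = 14.3%. For LOM at Week 28, the only scheduled draw date assigned to Period 2 reflects the Period 1 dose, and the only draw made on Period 2 drug goes to Part B.

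**Scale.** With about 25 patients per Period 2 arm, one patient is 1/25 = 4 percentage points. That is the unit of change, not an estimate of bias.

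**The case against.** The strongest reply is that SAP 9.3 already contains the right rule. Its closing sentence, read literally, keeps a pre-dose Week 24 event in Period 1, so the day clause is loose wording, and attribution by calendar day is a reasonable convention when only dates are recorded. The first half stands as far as it goes: the section contradicts itself. It does not settle the matter, because with dates alone the day clause is the version that can be programmed.

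Several limits also stand.

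- The documents do not say that a laboratory event takes the sample date as its onset. Events with an earlier recorded onset stay with the old treatment under either reading.
- A reader might infer that every safety assessment at Week 24 precedes the new drug. The documents say so only for laboratory samples. Footnote 14 covers entry to Part B alone.
- A reader might take 14% as the loss from the Period 1 tables. Those tables contain all patients on each dose, so the figures are 4.2% and 5.5%, and smaller as a share of all treatment-emergent events. Patients also count once per preferred term per phase, so some moved events change no count.
- A reader might infer that rates in the placebo and reduced-dose arms are pushed up. Those arms gain Week 24 events and lose LOM-visit events. The inflow is balanced in expectation between the two arms within a dose group, because re-randomisation is 1:1.
- The draw counts leave out unscheduled visits (Protocol 11.11).
- The laboratory change-from-baseline tables do not charge the transition-day value to the new drug, because it is the new baseline. The same holds for the tables of potentially clinically significant values where grading does not depend on baseline. All events are also listed by patient.

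**Conclusion.** The point holds for adverse events whose recorded onset is the transition date and which rest on assessments made before the new drug: laboratory results at Week 24, and all safety assessments at the LOM visit. For these, the day clause gives the wrong treatment. It conflicts with the closing sentence of the same section and with Protocol 12.1.

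It does not hold for every event on a transition day. A same-day event that does not come from a pre-dose assessment may belong to either treatment, and the day rule is a fair default for it.

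The sizes are 1/7 of responders' laboratory-detected Period 1 events (about 4% to 6% of all such events by dose group) and 1/k in Period 2. They rest on sample-day dating, equal detection at each draw and, for the dose-group figures, equal rates in responders and non-responders. The documents give no event rates, so the number of misassigned events cannot be stated, nor the net direction in the Period 2 arms. The study is descriptive and the effect is modest, but the rule should be corrected before the Part A freeze.

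**What to change.** Reconcile the two sentences in SAP 9.3:

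- For patients who continue, assign an adverse event to the preceding Part or Period if it is dated on the transition day and based on a pre-dose assessment of that visit. This covers at least the pre-dose laboratory results at both transitions, and all safety assessments at the LOM visit.
- Apply the same rule to Period 1 Day 1, where such events are pre-treatment.
- Keep the day rule for all other same-day events.
- Flag transition-day events in the adverse event listings.
- Resolve unclear cases by blinded review before the freeze.

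The cost is a wording change, one derivation flag and a small amount of blinded review. The review cannot be avoided, because dates alone do not show whether a same-day finding came before the dose.

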
PE = Physical Examination; HBV= hepatitis B virus; HCV = hepatitis C virus; SPRO = Satisfaction of Hair Patient Reported Outcome; QPRO = Quality of Hair Patient Reported Outcome; CGI-S = Clinical Global Impression of Severity; CGI-I = Clinical Global Impression of Improvement; PGI-S= Patient Global Impression of Severity; PGI-I = Patient Global Impression of Improvement;
 
 Day 1 (Visit 2) may occur any time after Screening laboratory results are available and reviewed by the Investigator.
 
 For Part A, Period 1, all subsequent visits and week increments should be based on the date of Visit 2. All visit windows are <math>\pm 2</math> days.
 
 Week 24 from Part A, Period 1 will also serve as the Day 1 visit for Part A, Period 2 for those who meet criteria to continue into the Dose Modification Phase.
 
 Also serves as the Early Termination Visit for patient withdrawal in this period.
 
 For Part A, Period 2, all subsequent visits and week increments should be based on the date of Week 24 (Visit 9). All visit windows are <math>\pm 2</math> days.
	
 The Safety Follow-Up Visit is intended as an Exit Visit for those subjects who discontinue the trial or for those who do not continue into the Open-label Extension study following completion of Part A, Period 1 or Part A, Period 2.
 
 Randomization and dispensation of study drug will occur on Week 24 only for those subjects who meet criteria and will continue into Part A, Period 2.
 
 Serum pregnancy test for females of childbearing potential only. Subjects who are surgically sterile or (hysterectomy or bilateral ligation) or post-menopausal (cessation of menses for at least 12 months prior to screening) need not be tested.
 
 Urine pregnancy test should be performed at the randomization visit.
 
 Includes hematology and serum chemistry, fasted.
 
 Collect pre-dose if subject is dosing in the clinic on study visit days.
 
 Will include thyroid stimulating hormone and hemoglobin A1c at Screening only.
 
 Includes total cholesterol, low-density lipoprotein, high-density lipoprotein, and triglycerides under fasted conditions.
 
 If SALT score <math>>20</math> at any visit in Part A, Period 2, patient will enter into Part B of the study and return to their original 8 mg BID or 12 mg BID dose from Part A, Period 1. However, all safety assessments outlined in Part A, Period 2 should be performed prior to dispensing study drug in Part B.
 
 Dispensation in Part A, Period 2 will only occur for subjects whose SALT remains <math>\leq 20</math>. If SALT <math>>20</math>, the subject should proceed to Day 1 (Visit B1).
 
 Day 1 (post-dose) and Weeks 12 and 24 (variable times post-dose)

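### SAP 9.3 has no rule for an adverse event with no start date that stops after the end of the last part entered; on the only end date the SAP defines, it defaults to Period 1 Day 1

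*SAP*

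**What the plan says.** SAP 9.3 (Adverse Events) gives a default for an event whose start day, month and year are all missing: "the start date will be set to the date of administration of study drug in Part A Period 1". There are three exceptions. If the event stopped before Period 1 dosing, the start is set to the stop date. The start moves to the Period 2 treatment start if "the stop date is between the start date of Part A Period 2 and the end date of Part A Period 2". It moves to the Part B treatment start if "the stop date is between the start date of Part B and the end date of Part B".

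A missing stop date has its own rule: "For an entirely missing stop date (i.e. day, month, and year are missing), the stop date will be imputed as the" patient's last visit date. The order in which start and stop dates are imputed is not stated.

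Section 9.3 does not define the end date of a Part or Period. SAP Section 4 defines the start: "Treatment start date for each part and period will be defined as the date of randomization or re-randomization". For the end it equates two terms: "the date of last dose (ie, treatment end date) will be imputed". Section 4 also mentions "the study discontinuation date of that part or period", but 9.3 does not use that term.

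The treatment-emergent definition in SAP 9.3 assigns an event to a Part/Period if it occurs after the first dose there and, for patients who go on, before the first dose of the next one. It sets no upper limit for the last Part/Period entered.

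**The concern.** Adverse events can stop after the last dose. Patients who do not enter the extension study return four weeks after Week 24. The schedule in SAP 15.2 says: "The Safety Follow-Up Visit is intended as an Exit Visit for those subjects who discontinue the trial", and it also covers those who do not roll over. Protocol 9.3 keeps patients who stop drug early in the planned visits. Protocol 12.3 follows adverse events without a fixed time limit. A missing stop date is imputed to the last visit, which for a follow-up attendee is after the last dose.

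If end date means last dose, none of these stop dates meets an exception, and the event reverts to Period 1 Day 1. The treatment-emergent tables are built by Part/Period and arm, and SAP 15.4 marks the Period 1 and Period 2 versions for the abbreviated report supporting the NDA. An event that the SAP's own scheme would place in a Period 2 or Part B column would then appear under Period 1.

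**Working it through.** The plan gives no figure to reproduce. The check applies the rule literally to an illustrative patient.

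**Inputs.** The 24-week periods and 4-week follow-up come from protocol 8.1, and the arm sizes from protocol 13.1. The day numbers are assumptions built on them:
- Period 2 patient: Period 1 on days 1–168, Period 2 from day 169, last dose day 336, Week 48 visit day 337, follow-up day 337 + 28 = 365.
- Part B patient with loss of maintenance at Week 12 of Period 2: Period 2 on days 169–252, Part B on days 253–420, Week 24 visit day 421, follow-up day 449.

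**Stop days after the last dose.** There are 365 − 337 + 1 = 29 for the Period 2 patient and 449 − 421 + 1 = 29 for the Part B patient. The number sent to Period 1 Day 1 depends on what end date means:

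| Reading of end date | Period 2 patient | Part B patient |
|---|---|---|
| Last dose (day 336; day 420) | 29 of 29 | 29 of 29 |
| Final on-treatment visit (day 337; day 421) | 28 of 29 | 28 of 29 |
| Study exit including follow-up (day 365; day 449) | 0 of 29 | 0 of 29 |

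If start dates are imputed before stop dates, an event with both dates missing goes to Period 1 on every reading.

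**Size of the shift in onset date.**
- Period 2: 169 − 1 = 168 days = 24 weeks. The column changes from reduced dose or placebo to Period 1 8 mg or 12 mg.
- Part B, example: 253 − 1 = 252 days = 36 weeks.
- Part B, range: entry at Week 4 to Week 24 of Period 2 gives 24 + 4 = 28 to 24 + 24 = 48 weeks. Part B restores the Period 1 dose, so the dose level is unchanged.

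**Effect on a percentage.** One patient is 1/25 = 4.0 points in a Period 2 arm, 1/170 = 0.6 points in the Period 1 8 mg arm and 1/130 = 0.8 points in the 12 mg arm. This assumes that the patient has no other event counted in the same table row.

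**Consistency with the treatment-emergent definition.** Take a patient whose last part is Period 2. An event with a known onset on day 350 is a Period 2 event under SAP 9.3. An event with no start date that stops on day 350 becomes a Period 1 event if end date is last dose. One rule leaves the last part open and the other closes it. Protocol 13.4.5 does end its treatment-emergent window at Week 24 or early termination, but the SAP does not carry that limit over, and SAP Section 2 gives the SAP primacy. The closing sentence of the imputation rules concerns partial dates and does not fill the gap.

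**The case against.** The strongest reply is that 9.3 speaks of the end date of the Part or Period, not of dosing, and that several places treat follow-up as belonging to a part. SAP Section 4 imputes a missing last-dose date from the last visit within a part that is not a follow-up visit. SAP 6.1 tabulates study completion by Part/Period with a safety follow-up category. Protocol Table 2 labels the Week 28 follow-up as a Part B visit. On that reading no stop day up to the follow-up visit is misplaced. This stands as a plausible intention, but the SAP never adopts it, and an event followed beyond study exit would still meet no exception.

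Three stronger inferences are tempting, and the documents do not support them:
- *The event is charged to the wrong treatment.* True onset is unknown and could have been in Period 1. The assignment is wrong only by the SAP's own convention, and the event is still counted as treatment-emergent and listed.
- *Two events ending a day apart can land on different drugs with onsets 48 weeks apart.* The 48 weeks arise only in Part B, where the dose is the Period 1 dose. Where treatment differs, in Period 2, the shift is 24 weeks.
- *Placement depends on whether the patient exits through follow-up or the extension study.* On the last-dose reading this requires the last dose to fall on the final visit day, which the documents do not fix. With the last dose on day 336 and the visit on day 337, an event imputed to the final visit goes to Period 1 by either route.

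It is also fair that few events should qualify. Protocol 12.2.4 requires start and stop dates for every event, and the data are queried.

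**Conclusion.** The gap is real, and the point is minor. As written, the rule does not cover a stop date after the end of the last part entered. On the best-supported meaning of end date, such an event defaults to Period 1 Day 1, contrary to the open-ended window in the same section. Only patients who entered Period 2 or Part B are affected, because Period 1 is the only treatment for everyone else.

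The conclusion rests on reading end date as last dose, or as the final on-treatment visit; the follow-up-inclusive reading removes most of the problem. The documents give no count of events without a start date, and it is probably very small. All safety summaries are descriptive, so no test is affected. What is at stake is the accuracy of small-arm tables, at about 4 points per affected patient in a Period 2 arm.

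**What to change.** In SAP 9.3, state that stop dates are imputed first, and replace the two closed windows with ordered, open-ended conditions for an entirely missing start date:
1. If the stop date is on or after the first Part B dose, set the start to the Part B treatment start.
2. Otherwise, if it is on or after the first Period 2 dose, set the start to the Period 2 treatment start.
3. Otherwise, use the Period 1 first dose, or the stop date if that is earlier.

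In the illustrations, stop days 169–365 then go to Period 2 and stop days 253–449 go to Part B, with none falling through. This matches the treatment-emergent definition, and the rule no longer needs a definition of end date. The cost is a sentence or two in the SAP and one programming condition, with no new data collection.
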